**6.3. Overview of Objectives and Endpoints**

**Table 6.3-1** provides an overview of the aforementioned study objectives and endpoints and a rationale for the specific endpoints.

**Table 6.3-1: Overview of Objectives and Endpoints**

Objective	Endpoint	Rationale for Endpoint
Primary Endpoint		
Evaluate effectiveness of the cerebral protection device during TAVR procedures	All stroke to 72 hours post-TAVR procedure	Demonstrate significant reduction of peri-procedural stroke (≤72 hours) after TAVR, which is a critical acute safety event observed in the population undergoing TAVR.
Additional Measurements of Safety and Effectiveness		
Evaluate safety of the cerebral protection device	Safety measures peri- and post- TAVR procedure and at discharge	Confirm safety based on assessments recommended by VARC  and NeuroARC  for this elderly population.

**Table 6.3-1: Overview of Objectives and Endpoints**

Objective	Endpoint	Rationale for Endpoint
Evaluate effectiveness of the cerebral protection device	Device performance and other effectiveness measures peri- and post TAVR procedure and at discharge	Effectiveness assessments recommended by VARC  and NeuroARC  for this elderly population.

Abbreviation: NeuroARC=Neurologic Academic Research Consortium; TAVR=transcatheter aortic valve replacement; VARC=Valve Academic Research Consortium

## 7. Study Design

[figure not shown]
PROTECTED TAVR is a prospective, post-market, multicenter randomized controlled trial (RCT) evaluating use of the Sentinel® Cerebral Protection System in subjects with aortic valve stenosis who are treated with an approved TAVR device.

### 7.1. Scale and Duration

An initial enrollment of up to 3000 randomized subjects in up to 100 study centers is planned (see **Note 1** below). A single center may enroll up to 15% of the total enrollment; approval from the Sponsor is required for additional enrollment. Subjects to be treated via a transfemoral approach with a commercially available TAVR device will be randomized 1:1 into a Test cohort using the commercially available Sentinel or a Control cohort with no cerebral protection system. A subject who provides an ICF signed by the subject or the subject’s legally authorized representative is considered enrolled in the study upon randomization, which will occur at the index procedure prior to procedural puncture/incision. The study duration for each subject is expected to be through 72 hours or hospital discharge, whichever comes first. In subjects diagnosed with a stroke, mRS must be administered at 30±7 days after the stroke. For these subjects, study duration will be through 30±7 days post stroke.

**Note 1:** If sample size re-estimation is needed (see Section **11.1.1.2**), the planned maximum enrollment will be up to 6000 randomized subjects.

**Figure 7.1-1** summarizes the study design. The treating physician must be a trained, experienced Sentinel user. Every subject must be deemed treatable with the Sentinel device (have suitable anatomy per the Sentinel Instructions For Use [IFU]). All eligible subjects (see Section **8**) should be approached for participation in the trial.

**Figure 7.1-1: PROTECTED TAVR Study Design Summary**

The planned initial enrollment of 3000 subjects is expected to be completed in approximately 30 months; therefore, the study duration is estimated to be less than 32 months (see **Note 1** in Section 6.2.2 regarding subjects diagnosed with a stroke). Enrollment may be extended based on the planned interim analysis (see Section 11.1.1.2).

The PROTECTED TAVR study will be registered at ClinicalTrials.gov prior to enrollment of the first subject.

## 7.2. Treatment Assignment

Subjects who are to be treated with a commercially available TAVR device and who have suitable anatomy for the Sentinel device will be randomized 1:1 into a Test cohort using the commercially available Sentinel or a Control cohort with no cerebral protection system. Randomization will occur at the index procedure (prior to procedural puncture/incision) to avoid selection/treatment bias. The randomization schedules will be computer-generated, using a pseudo-random number generator. Randomization will be stratified by center, by operative risk, and by intended TAVR valve type (Section 11.2.4). All randomized subjects will have unique identification numbers. Random permuted blocks will be employed to ensure approximate balance of treatment allocation within each stratum. Instructions on randomization are provided in the Manual of Operations. See Section 5 for a detailed description of the Sentinel device.

## 7.3. Justification for the Study Design

In order to support the stated objectives of this study (see Section 6.1) while also limiting the potential exposure of study subjects to risk, an initial enrollment of up to 3000 randomized subjects at up to 100 centers in North America, Europe, and Australia is planned. Treating physicians will be appropriately trained and have relevant clinical experience with the Sentinel device before enrolling trial subjects. Safety and effectiveness results will be reported on all enrolled subjects (see Section 19 for information on safety reporting). One planned formal interim analysis for the primary endpoint will be conducted on the first 70%

of enrolled subjects (N=2100). The study will be stopped early if a significant difference in favor of the test arm is observed after this interim analysis.

Management of subjects in both groups, including antiplatelet and anticoagulant medications, will be left to the discretion of the treating physician in this post-market study.

## 8. Subject Selection

Subjects will be evaluated for eligibility for commercial TAVR by the center heart team per the local standard of practice. All eligible subjects should be approached for participation in PROTECTED TAVR. Subjects who meet all of the inclusion criteria (see Section 8.1) will be evaluated for enrollment in this trial, provided no exclusion criterion (see Section 8.2) is met. All subjects will have unique identification numbers.

### 8.1. Inclusion Criteria

Subjects who meet all of the following criteria (**Table 8.1-1**) may be given consideration for inclusion in this clinical investigation, provided no exclusion criterion (see **Table 8.2-1**) is met.

**Table 8.1-1: PROTECTED TAVR Inclusion Criteria**

- |  |
|--|
| 
IC1. Subject has documented aortic valve stenosis and is treated with an approved transcatheter aortic valve replacement device via transfemoral access.
 
IC2. Subject has the recommended artery diameter at the site of filter placement per the Sentinel® Cerebral Protection System Instructions For Use: 9–15 mm for the brachiocephalic artery and 6.5–10 mm in the left common carotid artery as determined by computed tomography or per local standard of care.
 
IC3. Subject (or legal representative) provides written informed consent.
 |
|--|

### 8.2. Exclusion Criteria

Subjects who meet any one of the criteria in **Table 8.2-1** (listed as contraindications in the Sentinel® Cerebral Protection System IFU) will be excluded from this clinical study.

**Table 8.2-1: PROTECTED TAVR Exclusion Criteria**

- |   |
|---|
| 
EC1. Subject has arterial stenosis >70% in either the left common carotid artery or the brachiocephalic artery.
 
EC2. Subject's brachiocephalic or left carotid artery reveals significant stenosis, ectasia, dissection, or aneurysm at the aortic ostium or within 3 cm of the aortic ostium.
 
EC3. Subject has compromised blood flow to the right upper extremity.
 
EC4. Subject has access vessels with excessive tortuosity.
 
EC5. Subject has uncorrected bleeding disorders.
 
EC6. Subject is contraindicated for anticoagulant and antiplatelet therapy.
 |
|---|

**Note:** Use of general anesthesia during TAVR may affect neurocognitive function shortly after the

**Table 8.2-1: PROTECTED TAVR Exclusion Criteria**

procedure. While not an exclusion criterion, it is recommended that general anesthesia not be used if possible.

## 9. Subject Accountability

### 9.1. Point of Enrollment

A subject who provides an ICF signed by the subject or the subject's legally authorized representative is considered enrolled in the study upon randomization, which will occur at the index procedure prior to procedural puncture/incision.

### 9.2. Withdrawal

All subjects enrolled in the clinical study (including those withdrawn from the clinical study) shall be accounted for and documented. If a subject withdraws from the clinical investigation the reason(s) shall be reported. Reasons for withdrawal include but are not limited to physician discretion, subject choice to withdraw consent, or death. If such withdrawal is due to problems related to device safety or performance, the investigator shall ask for the subject's permission to follow his/her status/condition outside of the clinical study.

While all efforts will be made to minimize attrition, subjects may withdraw from the study at any time, with or without reason, and without prejudice to further treatment. Withdrawn subjects will not undergo any additional study follow-up, nor will they be replaced. The investigator may discontinue a subject from participation in the study if the investigator feels that the subject can no longer fully comply with the requirements of the study or if any of the study procedures are deemed potentially harmful to the subject. Data that have already been collected on withdrawn subjects will be retained and may be used for analysis, unless local regulations apply. No new data will be collected after subject withdrawal.

All applicable case report forms up to the point of subject withdrawal and an "End of Study" form for the subject must be completed. If the withdrawal is due to investigator discretion, the investigator should follow-up with the subject per standard of care.

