#### 11.1.1.4. Statistical Methods – Primary Endpoint

All subjects who are enrolled will be eligible for evaluation. Handling of dropouts and missing data will depend on their frequency and the nature of the outcome measure. Methods to eliminate or minimize bias will be implemented and described completely, if applicable. Outlier values will be evaluated for their validity. Suspected invalid data will be queried and corrected in the database prior to statistical analysis.

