## 19. Safety Reporting

### 19.1. Reportable Events by Investigational Center to Boston Scientific

It is the responsibility of the investigator to assess and report to BSC any event that occurs in any of following categories:

- All serious adverse events (SAE)
- All device-related adverse events
- All device deficiencies
- Unanticipated adverse device effects (UADE)/unanticipated serious adverse device effects (USADE)
- All CEC events (see below)
- New findings/updates in relation to already reported events

When possible, the medical diagnosis should be reported as the Event Term instead of individual symptoms.

If it is unclear whether or not an event fits one of the above categories, or if the event cannot be isolated from the device or procedure, it should be submitted as an adverse event (AE) and/or device deficiency.

Any AE required by the protocol, experienced by the study subject after informed consent and once considered enrolled in the study, whether during or subsequent to the procedure, must be recorded in the eCRF. Collection of safety events includes all CEC events (see below), regardless of seriousness and device relationship.

Underlying diseases are not reported as AEs unless there is an increase in severity or frequency during the course of the investigation. Death should not be recorded as an AE but should only be reflected as an outcome of one (1) specific SAE (see **Table 19.2-1** for AE definitions).

Refer to the Instructions For Use for the known risks associated with the commercial device.

The endpoints (see endpoint definitions in **Table 25.2-1**) requiring adjudication by the CEC include the following.

- Death: cardiovascular and non-cardiovascular
- Stroke: disabling and non-disabling
- Transient ischemic attack
- Delirium
- Acute kidney injury (Stage 2 and Stage 3)
- Sentinel access site major vascular complications related to the procedure

Details on the CEC events and procedures are outlined in the CEC charter. Tests and images required to adjudicate these events are specified in the event definitions (see **Table 25.2-1**).

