STROKE NeuroARC   Neurological Event Definitions	
  
 Type	Description	
   
 Type 1 – Overt CNS Injury: Acutely Symptomatic Brain or Spinal Cord Injury	
 
 Type 1.a Ischemic stroke	                             Sudden onset of neurological signs or symptoms fitting a focal or multifocal vascular territory within the brain, spinal cord, or retina, that:                             
 
1. Persist for ≥24 h or until death, with pathology or neuroimaging evidence that demonstrates either:                                     
 
a. CNS infarction in the corresponding vascular territory (with or without hemorrhage); or
 
b. Absence of other apparent causes (including hemorrhage), even if no evidence of acute ischemia in the corresponding vascular territory is detected
 
 
 
                             or                         	
  
	Type	Description	Type 1 – Overt CNS Injury: Acutely Symptomatic Brain or Spinal Cord Injury		Type 1.a Ischemic stroke	Sudden onset of neurological signs or symptoms fitting a focal or multifocal vascular territory within the brain, spinal cord, or retina, that: 
 
1. Persist for ≥24 h or until death, with pathology or neuroimaging evidence that demonstrates either:                                     
 
a. CNS infarction in the corresponding vascular territory (with or without hemorrhage); or
 
b. Absence of other apparent causes (including hemorrhage), even if no evidence of acute ischemia in the corresponding vascular territory is detected
 
 
 
 or
	Type	Description					
	Type 1 – Overt CNS Injury: Acutely Symptomatic Brain or Spinal Cord Injury						

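### Section 9.2 ends data collection for every kind of withdrawal, not only withdrawn consent, and so can leave primary-endpoint strokes unrecorded in the ITT set

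*Combined protocol and SAP*

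**What the plan says.** Section 9.2 (Withdrawal) sets one rule for several different situations.

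- Reasons: "Reasons for withdrawal include but are not limited to physician discretion, subject choice to withdraw consent, or death". The investigator may also discontinue a subject on judging that "the subject can no longer fully comply with the requirements of the study".
- Consequence, with no exception by reason: "Withdrawn subjects will not undergo any additional study follow-up, nor will they be replaced", and "No new data will be collected after subject withdrawal".
- Device safety or performance problems: the investigator asks permission to "follow his/her status/condition outside of the clinical study". After withdrawal at investigator discretion, follow-up is left to standard of care. Neither route is said to feed the study database.
- Data collected before withdrawal are retained and may be analyzed, subject to local regulations. Case report forms up to that point must be completed.

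Other sections point the other way. Section 10.6 requires safety and CEC events to be reported from enrollment through 72 hours or discharge, and Section 10.8 says all subjects are followed that long. Section 19.1 lists "New findings/updates in relation to already reported events" among reportable items. Section 11.2.1 puts every randomized subject in the ITT set. None of these mentions withdrawal. On missing outcomes, Section 11.1.1.4 says only: "Handling of dropouts and missing data will depend on their frequency and the nature of the outcome measure".

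**The concern.** An ITT comparison of stroke proportions needs the outcome of every randomized subject. Withdrawal of consent to data collection is a reason to stop collecting. An investigator's decision to discontinue, or a device problem, is not in itself such a reason, yet Section 9.2 gives all of them the same consequence.

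Two features make this more than untidy wording. First, the person deciding can know the arm. Section 10.6 asks only that the neurological assessor be blinded; no blinding is described for the investigator. Withdrawal for device problems should by inference arise mainly in the Test arm, because the study device is Sentinel and Control subjects receive none. Second, the endpoint depends on information that arrives after onset. The main limb of NeuroARC Type 1.a in Table 25.2-1 requires signs that "Persist for ≥24 h or until death, with pathology or neuroimaging evidence that demonstrates either" infarction or no other apparent cause. A subject with a new deficit may also be among those least able to complete the scheduled tests.

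At stake is the completeness of a primary endpoint with few events: about 60 in Control and 30 in Test at the design rates.

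**Working it through.** **1. The sections side by side.** Consider a subject discontinued by the investigator 20 hours after TAVR and still in hospital. Sections 10.6 and 10.8 call for event reporting to 72 hours or discharge. Section 9.2 forbids new data. Section 11.2.1 keeps the subject in the analysis. If a stroke begins at 40 hours, a site that follows 9.2 literally does not record it. If a deficit began at 18 hours and imaging follows at 30 hours, the onset is on file but the confirming evidence is not. A stroke fully documented before hour 20 is retained.

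**2. The plan's own figures.** Inputs from Sections 11.1.1.2 and 11.3.2: 4% versus 2%, 1500 per arm, one look at 70% (1050 per arm), nominal two-sided levels 0.0148 and 0.0455, chi-square test.

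- Lan-DeMets O'Brien-Fleming spending at t = 0.7, with 0.025 per tail: 4 × [1 − Φ(2.2414/√0.7)] = 0.0148. The matching final level is 0.0455. Both reproduce.
- Group sequential power without sample size re-estimation is 89.1%. The stated figure of more than 0.90 includes re-estimation under a charter rule, so the excess cannot be checked.
- Expected strokes: 1500 × 0.04 = 60 and 1500 × 0.02 = 30, P = 0.0013.

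**3. Sensitivity near the boundary.** For 60 versus 40 strokes, the pooled proportion is 100/3000 = 0.03333.

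z = (20/1500) / √(0.03333 × 0.96667 × 2/1500) = 2.034, P = 0.042, below 0.0455.

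For 60 versus 41, P = 0.054, which fails. Likewise 50 versus 32 gives P = 0.044 and 50 versus 33 gives P = 0.058.

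**4. Error rate under assumed losses.** Simulated two-look trials used uncorrected chi-square tests at 0.0148 and 0.0455 and no sample size increase. The true rate is 4% in both arms. A lost stroke is counted as no stroke. Both the loss shares and that counting rule are assumptions.

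| Strokes lost | False success for Sentinel |
|---|---|
| None | 2.5% |
| 10% in both arms | 2.5% |
| 1% in Test only | 2.8% |
| 5% in Test only (3 of 60) | 4.6% |
| 10% in Test only (6 of 60) | 8.1% |
| 10% in Control only | 0.6% |

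An exact calculation at the final look alone gives 2.3%, 4.3% and 7.6% for Test-only losses of 0, 5% and 10%, the same pattern.

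**5. Power under assumed losses.** At 4% versus 2% (exact, final look only), power falls from 89.5% to 85.9% if 10% of strokes are lost in both arms, and to 75.1% if 10% are lost in Control only.

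**The case against.** The case for leaving the text alone has real force.

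- The non-compliance clause is permissive. For suspected stroke the protocol asks for more data: a neurology consult and, once stroke is diagnosed, an mRS at 30±7 days with mortality and device-event reporting (Sections 10.6 and 10.7). Nothing equates inability to complete a test with non-compliance.
- Events during the procedure must be reported (Section 10.5), CEC events are reportable through the end of the study, and their source documents are due when available (Table 19.4-1). A stroke that prompts withdrawal has therefore already become reportable.
- The window is at most 72 hours in hospital, so withdrawals may be few. If withdrawal were unrelated to stroke, losing 3 of 60 Test strokes would take about 5% of 1500, or 75, Test withdrawals.
- Any binary endpoint turns on one event at its boundary; the design rates are far from it.

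These points limit the size of the problem. They do not remove it, because none of the reporting sections says that it prevails over Section 9.2 after withdrawal.

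A reader might infer four stronger things that the documents do not support.

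- *That the rule favors Sentinel.* No passage counts a withdrawn subject as stroke-free, and non-compliance withdrawals can occur in either arm. The Test-only rows above result from assuming Test-only loss.
- *That a stroke subject withdrawn early cannot meet Type 1.a.* The definition also accepts symptoms under 24 hours with confirmed infarction, so imaging before withdrawal suffices.
- *That a Test stroke after a device problem never reaches the database.* That requires an actual withdrawal, and onset or evidence after it.
- *That naming death as a withdrawal reason bars later pathology.* This is a literal reading at odds with Section 19.1 and Table 19.4-1; it is an ambiguity to reconcile.

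**Conclusion.** The point holds as a defect in a stated rule. Section 9.2 does not separate withdrawal of consent from discontinuation by an investigator or over a device problem, and literal compliance stops collection of primary-endpoint data on subjects who stay in the ITT set. The exposure is confined to strokes with onset after withdrawal and to suspected strokes whose persistence or imaging is established after it.

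Its size is unknown. The documents give no withdrawal rate, and the study-specific SAP and CEC charter to which the protocol refers might address the handling; their text is not in the combined document. The illustrative false-success range of 0.6% to 8.1%, against 2.5% with complete data, shows that the result depends on which arm loses strokes. Equal loss costs power and leaves the error rate unchanged. The greater Test-arm share of device-related withdrawals is an inference. The change is worth making because a few unrecorded events could matter and the subjects are still in hospital when the data arise.

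**What to change.** Amend Section 9.2 to separate stopping study procedures from stopping data collection.

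1. Only a subject's explicit withdrawal of consent to further data collection ends collection, subject to local regulations.
2. For subjects discontinued by the investigator, subjects who decline further study procedures, and device-related withdrawals, keep recording the CEC events stroke, TIA, delirium and death, together with device-related events, in the study database. Take them from the hospital record through 72 hours or discharge.
3. Replace the provision for following device-related withdrawals outside the study with in-study recording under item 2.
4. State that source documents for events with onset before withdrawal or death are still collected for the CEC, which reconciles Section 9.2 with Section 19.1.

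The 30±7-day mRS in withdrawn subjects is not needed for the primary endpoint and can be optional.

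Planned N, alpha levels and clinical care do not change, and the required recording needs no extra visit within the endpoint window. The cost is a protocol and consent-form amendment, with ethics committee approval and translations where used, at up to 100 centers, plus the record review itself.

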### 9.3. End-of-Study Definition

This clinical study will be considered completed when the last subject has concluded assessments as outlined in the data collection schedule in **Table 10.1-1** (see **Note 1** below).

[figure not shown]
**Note 1:** In subjects diagnosed with a stroke, mRS must be administered at 30±7 days after the stroke; mortality plus device related adverse events (including adverse device effects [ADE], serious adverse device effects [SADE], unanticipated adverse device effects [UADE], and unanticipated serious adverse device effects [USADE]; see Section 19) through 30±7 days post stroke must be reported to BSC. For these subjects, study duration will be through 30±7 days post stroke.

